9.12 BIAS

To assess potential channeling bias baseline characteristics of all patients fulfilling the in/exclusion criteria and were included in SITS-AF registry in the defined time period will be described based on the treatment they receive for stroke prevention in NVAF within 3 months of the index event.

Differences in the patients that are initiated with dabigatran versus patients initiating with VKA, Factor Xa Inhibitors or no oral anticoagulation therapy will be described and set in context to the observed results in the dabigatran treated patient set (see also [Section 9.9](#)).

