6.1 Primary Analysis

This analysis will be done for NVAF patients presenting with first ischemic acute stroke and treated with dabigatran within 3 months of index event.

To describe the distribution of dabigatran treatment initiation times in patients with non-valvular atrial fibrillation (NVAF) after hospitalization for first-ever ischemic stroke (the index event) treated with dabigatran, we will

1. Create a histogram of initiation times by day.
2. Calculate mean, standard deviation and 95% (Standard Normal) confidence intervals (CI) of the Mean, as well as the median, interquartile ranges, minimum and maximum values.
3. Create frequency table by time periods. Give the absolute count of subjects and the proportion of subjects in each group. The time periods to be considered are 0-24h, >24-72h, >3-7d >7-14d, >14-28d, >28d-3m, however these categories may be revised depending on the distribution of initiation times to ensure sufficient patient numbers in each category.

We do not expect to have any missing values in the time to dabigatran treatment initiation. However, if there are missing values collected, they will be summarized in the frequency table as a separate category. Proportions for all other categories will not include the missing values in the denominator (as this is what has been done in previous works for all previous SITS-MOST and/or SITS-ISTR publications [P07-00880, P08-11746].). The proportion of missing values will be out of all subjects sampled.

6.2 Secondary Analysis:

These analyses will be done for NVAF patients presenting with first ischemic acute stroke and treated with dabigatran within 3 months of index event.

6.2.1 To describe baseline characteristics for patients treated with dabigatran according to time of dabigatran initiation.

Descriptions will only be done for the subgroups (of time to initiation) consisting of at least 100 patients. We Will:

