2. Make frequency tables of reasons by time period for each physician response with time periods as defined in the primary analysis. Time periods with less than 100 patients will not be considered. Comparisons of the distribution of reasons between different time periods may be made and a standardized difference of 10% or more in absolute value will be considered notable.
3. Make frequency tables of time periods by physician responses (reasons) with time periods as defined in the primary analysis. Reasons with less than 100 patients will not be considered. Comparisons of the distribution of time periods between different reasons may be made and a standardized difference of 10% or more in absolute value will be considered notable.

For Question 2 ("Reasons for not planned to start oral anticoagulation therapy"), a descriptive analysis (frequency tables of physician responses) will be done for NVAF patients presenting with first ischemic acute stroke and not receiving any OAC within 3 months of index event.

6.2.3 To describe self-reported factors important for the physician's decision as to the dose of dabigatran in the post-ischemic stroke setting.

For NVAF patients presenting with first ischemic acute stroke and treated with dabigatran within 3 months of index event, we will:

1. Make frequency tables for physician responses to question "Reasons for the dose of oral anticoagulation"
2. Make frequency tables for physician responses (reasons) for each dose categories 110, or 150 mg 2 times daily. Comparisons of the distribution of reasons between the dose categories may be made and a standardized difference of 10% or more in absolute value will be considered notable. Subgroup analysis for dose will only be performed if there are at least 100 patients in the subgroup
3. Make frequency tables for dose category (110, or 150 mg 2 times daily) for each physician response (reason) with at least 100 patients. Comparisons of the distribution

of dose between the reasons provided may be made and a standardized difference of 10% or more in absolute value will be considered notable.

:

7 Appendixes

7.1 Appendix 1

SITS Variables names particularly important for this study

Patient/ file code
Country name
Hospital/ Centre code
Gender
Age At Stroke Onset
Participation In Other Trials
Treatment at baseline
Aspirin
Dipyridamole
Clopidogrel
Other Antiplatelet
Anticoagulants- Yes/ No/ Unknown

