▪ Warfarin derivatives
▪ New OAC (NOAC)
• If NOAC
○ Dabigatran
○ Apixaban
○ Rivaroxaban
2h follow up
Systolic Blood Pressure
Diastolic Blood Pressure
NIHSS
24h follow up
NIHSS
Systolic Blood Pressure
Diastolic Blood Pressure
Current Infarct CT/MR
ASPECTS Score CT/MR
Local Haemorrhage CT/MR
Remote Haemorrhage CT/MR
Cerebral Oedema CT/MR
At discharge/ 7d
Diagnosis of NVAf at (previous, at or during hospital stay)
Oral anticoagulation (OAC) at = YES
▪ Warfarin derivatives
▪ New OAC (NOAC)
• If NOAC
○ Dabigatran
○ Apixaban
○ Rivaroxaban
Date & time of OAC start: DD/MM/YYYY, time: clock
OAC at discharge = No
1) Date of foreseen start of OAC if not started during hospital stay
Date: DD/MM/YYYY
Aspirin
mRS Score
NIHSS
Systolic Blood Pressure
Diastolic Blood Pressure
Date of
Dipyridamole
Clopidogrel
Other Antiplatelet

Anticoagulants Oral
Dabigatran
Dabigatran Dose
Date of Dabigatran Initiation
Anti Diabetic Oral
Antihypertensive Oral
Statin
Other
Type Of Stroke
Type Of Stroke Ischemic
Type Of Stroke Haemorrhagic
Date Time Of Death
Cause Of Death
At 3-months
Modified Rankin Scale score
If mRS=6=Dead, date/time of death
Cause of death
Patients with NVAf at discharge/ 7d but patient has not been prescribed Warfarin or NOAC (Dabigatran, Apixaban, Rivaroxaban at
1) Has the patient been prescribed Dabigatran after discharge?
If YES questions below will also be shown.
2) Date of initiation of Dabigatran for stroke prevention in NVAf
Date: DD/MM/YYYY
Dose:
Patients with NVAf has been prescribed dabigatran at discharge
Is the patient continuing the prescribed Dabigatran at 3 months follow up since start of the treatment?
- Yes/ No/ Unknown
If No, date of stop of treatment:
Reason for stop of treatment:
- Has the OAC treatment been changed?
If Yes,
Which treatment:

7.2 Appendix 2

CHADS₂ Stroke Risk Score

CHADS ₂ components	Points
Congestive heart failure	1
Hypertension	1
Age 75 years or older	1
Diabetes mellitus	1
Prior cerebral ischemia (i.e., stroke, TIA)	2
Maximum score	6

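### On the variables listed in SAP Appendix 1, only dabigatran has a 3-month start item, and only for patients without OAC at discharge/7d, so groups defined over 3 months cannot be built as described

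*SAP*

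**What the plan says.** Three analyses define treatment over 3 months. SAP 6.1 takes as its population patients "treated with dabigatran within 3 months of index event", with no condition on OAC status at discharge. SAP 6.2.2 analyses Question 2 (reasons why OAC was not planned) in patients "not receiving any OAC within 3 months of index event". Protocol 9.12 describes baseline characteristics of dabigatran, VKA, factor Xa inhibitor and no-OAC patients "based on the treatment they receive for stroke prevention in NVAF within 3 months of the index event", as a check on channelling.

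SAP Appendix 1 lists the variables. The discharge/7d form records OAC use, drug and start date. For patients not yet on OAC it adds "Date of foreseen start of OAC if not started during hospital stay". The 3-month form has two treatment blocks:

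- **Block A** is for patients with NVAF at discharge/7d "but patient has not been prescribed Warfarin or NOAC". It asks "Has the patient been prescribed Dabigatran after discharge" and, if so, the date and dose.
- **Block B** is headed "Patients with NVAf has been prescribed dabigatran at discharge". It asks about continuation, stop date and reason, then "Has the OAC treatment been changed" and to which treatment.

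Protocol 9.4 places the discharge record at day 7, or at discharge if that comes sooner. Protocol 9.1 says that dabigatran starts and stops will be assessed at discharge and at 3 months, without limiting this by OAC status at discharge.

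**The concern.** The group definitions assume that every OAC start and switch up to 3 months is known. The listed items do not supply this for two kinds of patient: those discharged on another OAC, and those who start another OAC after discharge.

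For the primary outcome, the patients lost are those who reach dabigatran after discharge/7d by way of another drug. They are late starters by construction, so losing them moves the distribution towards early initiation. The missing-value rule in SAP 6.1 would not reveal this. It deals with patients already in the population whose time is blank, whereas these patients never enter it.

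For the channelling comparison, dabigatran would be ascertained up to 3 months, but VKA and factor Xa inhibitors only up to discharge/7d. Late starters of those drugs would fall into the untreated group. The error may be related to stroke severity. Protocol section 7 says that warfarin start depends on severity and may come 3-4 weeks after a large stroke, well after the discharge/7d record. Severity is among the characteristics by which patients are to be described.

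Neither document mentions the problem. The limitations in SAP section 5 cover death, second stroke and leaving care. The ENCePP checklist answers No on information bias.

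**Working it through.** The plan gives no figure on this point to reproduce. The check is a trace of patient routes, followed by arithmetic on assumed rates.

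**1. Trace.** Each OAC status at discharge/7d is followed through the listed 3-month items.

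| At discharge/7d | Later, by 3 months | Listed 3-month item | Result |
|---|---|---|---|
| No OAC | Starts dabigatran | Block A, with date and dose | Captured |
| No OAC | Starts VKA or factor Xa inhibitor | None | Counted as no OAC |
| VKA or factor Xa inhibitor | Moves to dabigatran | None | Absent from primary population |
| Dabigatran | Moves to another OAC | Block B | Captured |

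The foreseen start date on the discharge form does not close the second row. It is a plan, it names no drug, and the listed 3-month items confirm only a dabigatran start.

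**2. Primary timing distribution.** Inputs: about 1000 dabigatran patients (Protocol 9.5). Assumed: a share *m* of true initiators is missed by the third route, and all of them start after day 7. (A patient discharged before day 7 could switch sooner, so this is a worst case for that cut-off.) Let *p* be the observed share starting after day 7, also assumed.

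True number = 1000 / (1 − *m*). True late share = *p*(1 − *m*) + *m*.

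| *m* | True number | *p* = 20% | *p* = 40% | *p* = 60% |
|---|---|---|---|---|
| 2% | 1020 | 21.6% | 41.2% | 60.8% |
| 5% | 1053 | 24.0% | 43.0% | 62.0% |
| 10% | 1111 | 28.0% | 46.0% | 64.0% |

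Example: 0.40 × 0.90 + 0.10 = 0.46. For *p* = 40% the understatement runs from 1.2 to 6.0 percentage points.

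**3. No-OAC group.** Assumed: a share *q* of patients recorded as no OAC started a VKA or factor Xa inhibitor after discharge. Truly untreated per 1000 recorded = 1000(1 − *q*). For *q* = 5%, 10%, 20% and 30% this is 950, 900, 800 and 700.

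**4. Patients without a 3-month record.** Protocol 9.9 expects about 20% loss to follow-up at 3 months. Whatever the form contains, these patients cannot be confirmed as untreated over 3 months.

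**The case against.** The strongest objection is that Appendix 1 is not the registry form. Its title presents the variables as especially important ones. It is demonstrably incomplete, since the physician-reason items in SAP 3.3 are said to be in the database yet do not appear there. Protocol 9.1 also promises dabigatran starts and stops without restriction. In the text available to us the condition for Block A breaks off mid-line. Protocol 9.7.2, to which the ENCePP checklist refers for exposure time windows, is not in that text either. All this stands: the documents do not show that the registry lacks the fields. They show that the variables listed for the study do not support the definitions used in it.

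A reader might go further and infer that the 3-month items ask only about dabigatran and only in patients discharged without OAC. That is not supported. Block B covers patients on dabigatran at discharge and records a change of OAC and the new treatment, so switches away from dabigatran are seen. The change question might be meant for all OAC patients. However, it sits under the dabigatran heading and has no start date or dose for the new drug, so it would not supply a time to initiation.

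The consequences are also bounded. Question 2 asks why OAC was not planned, so few of its respondents may have started later. The channelling comparison concerns baseline characteristics only, and no outcome comparison by treatment is planned. These points limit the harm but do not make the group labels correct.

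Another tempting remedy is to restrict the main population to patients whose first OAC after the stroke was dabigatran. That goes too far, because it would drop patients switched to dabigatran in hospital, whom the discharge items do record.

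**Conclusion.** The point holds for the listed variables. The only initiation item at 3 months concerns dabigatran, in patients without a warfarin or NOAC prescription at discharge/7d. Groups built from Appendix 1 as written would omit later switchers to dabigatran from the primary population. They would also count late VKA and factor Xa inhibitor starters as untreated in the channelling comparison, and possibly in the Question 2 group.

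The direction for the primary outcome is clear: missed patients start after discharge/7d, so the distribution leans early. The size is unknown, because the documents give no rate of switching or late starting. The figures above only show how the error scales with assumed rates, and a reader should not infer from them that a large share of patients is in fact missing. Confidence is moderate, because the list may be incomplete and the Block A condition is cut off. The correction should be made: it is cheap, and the affected groups carry the primary result and the main check on channelling.

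**What to change.** Confirm whether the registry records any OAC start or switch, with drug and date, up to 3 months for all NVAF patients.

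- **If it does:** add those variables to SAP Appendix 1 and define the groups from them.
- **If it does not:**
  - Restate the main population as *dabigatran recorded by discharge/7d, or started after discharge in patients with no OAC at discharge/7d*.
  - Relabel the remainder, including the Question 2 group, *no OAC at discharge/7d and no dabigatran recorded by 3 months*.
  - Present the channelling comparison for all drugs by status at discharge/7d, with later dabigatran starters as a separate group.
  - State in SAP section 5 that later switches to dabigatran and later VKA or factor Xa inhibitor starts are not observed, and that the timing distribution may lean early as a result.

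The cost is one query to the registry and changes to SAP wording and table labels, with no new data collection. The downside of the second branch is that the channelling comparison then refers mainly to discharge/7d rather than to 3 months.
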